Thus, the SPIRIT IV trial was performed with clinical endpoints only and represents an adequately-powered, single- blind, multicenter prospective trial comparing the XIENCE V stent to the TAXUS EXPRESS stent in 3690 subjects (2:1 ratio of XIENCE V to TAXUS EXPRESS). The primary endpoint was target lesion failure (TLF) defined as the composite of cardiac death, target vessel MI and ischemia-driven target lesion revascularization (TLR), and was superior for XIENCE V stent compared to TAXUS EXPRESS stent (TLF 3.9% vs. 6.6%, respectively, P=0.0008).⁵⁰ In addition, both TLR (2.5% vs. 4.6%, P=0.001), MI (1.9%. vs. 3.0%, P=0.02), and ARC definite or probable stent thrombosis (ST) (0.29% vs. 1.06%, P=0.003) favored the XIENCE V stent group. These results were duplicated in the investigator-sponsored COMPARE trial (also performed without routine angiographic follow-up), in which 1800 subjects were randomized to the XIENCE V stent vs. the TAXUS Liberté stent.²¹ Compared to TAXUS at one year, XIENCE V stent resulted in statistically lower rates of the primary composite endpoint of death, MI or TVR (6.2% vs. 9.1%, P=0.02), as well as MI (2.8% vs. 5.4%, P=0.007), ARC definite or probable ST (0.7% vs. 2.6%, P=0.002), TLR (1.7% vs. 4.8%, P=0.0002).

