5.2. Other Secondary Endpoints

The primary endpoint composite event rate (all-cause death, MI or stroke) and powered secondary endpoints at all time points other than median of 3 years will be other secondary endpoints.

Time points for all other secondary endpoints, unless specified otherwise, are in-hospital, 30 days, 6 months, 1, 2, 3, 4, and 5 years post-procedure. The other secondary endpoints are:

- All-cause mortality
 - Cardiac death
 - Non-cardiac death
- All MI (peri-procedural, spontaneous, Q-wave and non Q-wave) including large and small MIs
- Protocol-defined MI
- MI adjudicated per Universal MI Definition
- Stroke (all, ischemic, and hemorrhagic)
- Disability following stroke event at 90 days± 2 weeks

- Ischemia-driven revascularization
 - Ischemia-driven target lesion revascularization (TLR)
 - Ischemia-driven target vessel revascularization (TVR)
 - Ischemia-driven non target vessel revascularization (Non-TVR)
- All revascularization (ischemia driven and non-ischemia driven)
 - All target lesion revascularization (TLR)
 - All target vessel revascularization (TVR)
 - All non-target vessel revascularization (non-TVR)
- Complete revascularization at baseline procedure, anatomic and functional (see Section 19. Appendix D).
- Stent thrombosis (ARC definition) symptomatic or asymptomatic
- Symptomatic graft stenosis or occlusion (since this requires angiographic documentation, this endpoint will be compared to symptomatic ARC definite stent thrombosis)
- Bleeding complications
 - Requirement for blood product transfusion
 - TIMI scale (major or minor)
 - BARC scale
- Requirement for blood product transfusion
- Time from randomization to procedure; time from procedure to discharge; ICU days; time from procedure to return to work
- Major adverse events (MAE) defined as composite of the following components. MAE will be assessed in-hospital and at 30 days only.
 - death
 - myocardial infarction
 - stroke
 - Transfusion of ≥ 2 units of blood
 - TIMI major or minor bleeding
 - major arrhythmia
 - unplanned coronary revascularization for ischemia
 - any unplanned surgery or therapeutic radiologic procedure
 - renal failure
 - sternal wound dehiscence
 - infection requiring antibiotics for treatment
 - intubation for >48 hours
 - post-pericardiotomy syndrome.

Definitions of terms and endpoints are located in Sections 16.1 and 16.2. Acronyms and abbreviations are defined in Section 16.0. Other secondary endpoints are included in the QoL sub-study.

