8.3.2. Follow-up Angiography

Routine follow-up angiography in the asymptomatic subject is not permitted in this study. Prior studies have not demonstrated a benefit of routine follow-up angiography after ULMCA disease, and routine follow-up angiography can result in non clinically indicated revascularization procedures (the "oculostenotic reflex").^{48,49} In the SYNTAX trial, routine follow-up angiography was performed at 15 months in 268 surviving asymptomatic subjects with ULMCA disease randomized to PCI with TAXUS PES vs. CABG. In the PCI group, the mean late loss in the left main stem with PES was only 0.2 mm, and thrombus was present in only 2 subjects (1%). The composite rate of death, MI, stroke or repeat revascularization among PCI subjects undergoing routine angiography was 13% at 15 months (compared to 15.8% in all PCI subjects at 12 months, including those who were symptomatic). Numerous prior studies of drug-eluting stents in subjects with ULMCA disease have demonstrated very low rates (<0.5%) of left main stent thrombosis,^{25, 72, 73} and no prior study of routine angiographic follow-up has been shown to improve outcomes after drug-eluting stents. Routine angiographic follow-up after left main intervention is not recommended by the current ACC/AHA PCI guidelines.²⁷

For subjects who develop atypical chest pain or other symptoms that might reflect ischemia, it is strongly recommended that a nuclear stress test, echocardiographic stress test, or MSCT scan be performed, with subsequent angiography only for positive non-invasive results. Valid indications for follow-up angiography in the present study include any of the following:

- the recurrence of typical angina;
- a positive noninvasive study indicating moderate or severe ischemia, a significant decline in left ventricular function or progressive valve disease;
- progressive heart failure or unstable arrhythmias;
- cardiac arrest;
- or other clinical conditions for which the treating physician believes follow-up angiography is indicated.

The reasons for follow-up angiography will be closely tracked in the case report form.

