Non-Target Vessel: For the purposes of this trial, the only possible non-target vessel would be the right coronary artery and its major branches that were not treated by either PCI or CABG at the index procedure (unless either the LAD or LCX are occluded at baseline and no attempt was made to revascularize these territories by either PCI or CABG).

Target Vessel Revascularization (TVR): Target vessel revascularization is any repeat percutaneous intervention of the target vessel or bypass surgery of the target vessel

Target Lesion Revascularization (TLR): Target lesion revascularization is defined as any repeat percutaneous intervention of the target lesion or bypass surgery of the target vessel

All revascularization events will be adjudicated as either ischemia-driven or non ischemiadriven

Ischemia-Driven Target Lesion (or Vessel) Revascularization: A target lesion (vessel) revascularization will be considered ischemia-driven if the target lesion diameter stenosis is \geq 50% by QCA (analysis segment measurement, involving the lesion itself and 5 mm of proximal and/or distal margin) and any of the following criteria for ischemia are met:

- A positive functional study corresponding to the area served by the target lesion; or
- Ischemic ECG changes at rest in a distribution consistent with the target vessel; or
- Typical ischemic symptoms referable to the target lesion; or
- IVUS of the target lesion with a minimal lumen area (MLA) of ≤4mm² for non left main lesions or ≤6mm² for left main lesions. If the lesions are *de novo* (i.e. not restenotic), the plaque burden must also be ≥60%; or
- FFR of the target lesion ≤ 0.80
Note: A target lesion revascularization for a diameter stenosis less than 50% might also be considered ischemia-driven by the CEC if there was a markedly positive functional study or ECG changes corresponding to the area served by the target lesion.

Ischemia-Driven Non-Target Vessel Revascularization: A non target vessel revascularization will be considered ischemia-driven if any lesion the non target vessel has a diameter stenosis \geq 50% by QCA with any of the above criteria for ischemia met.

Unplanned revascularization for ischemia: Any repeat revascularization of either a target vessel or non-target vessel with any of the above criteria for ischemia met.

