*Acute or subacute can also be replaced by the term early stent thrombosis. Early stent thrombosis (0 to 30 days) will be used in the remainder of this document.

[†]Includes primary as well as secondary late stent thrombosis; secondary late stent thrombosis is a stent thrombosis after a target lesion revascularization.

2. ARC Definitions of Definite, Probable, and Possible Stent Thrombosis

• Definite Stent Thrombosis

Definite stent thrombosis is considered to have occurred by *either* angiographic or pathological confirmation:

a. Angiographic confirmation of stent thrombosis

The presence of a thrombus[‡] that originates in the stent or in the segment 5 mm proximal or distal to the stent and presence of at least 1 of the following criteria within a 48-hour time window:

- 1. Acute onset of ischemic symptoms at rest
- 2. New ischemic ECG changes that suggest acute ischemia

- 3. Typical rise and fall in cardiac biomarkers (refer to definition of spontaneous MI: Troponin or CK-MB > 99th percentile of URL)
- 4. Nonocclusive thrombus
 - a. Intracoronary thrombus is defined as a (spheric, ovoid, or irregular) noncalcified filling defect or lucency surrounded by contrast material (on 3 sides or within a coronary stenosis) seen in multiple projections, or persistence of contrast material within the lumen, or a visible embolization of intraluminal material downstream
- 5. Occlusive thrombus
 - a. TIMI 0 or TIMI 1 intrastent or proximal to a stent up to the most adjacent proximal side branch or main branch (if originates from the side branch)
- b. Pathological confirmation of stent thrombosis

Evidence of recent thrombus within the stent determined at autopsy or via examination of tissue retrieved following thrombectomy

• Probable Stent Thrombosis

Clinical definition of probable stent thrombosis is considered to have occurred after intracoronary stenting in the following cases:

a. Any unexplained death within the first 30 days

b. Irrespective of the time after the index procedure, any MI that is related to documented acute ischemia in the territory of the implanted stent without angiographic confirmation of stent thrombosis and in the absence of any other obvious cause

• Possible Stent Thrombosis

Clinical definition of possible stent thrombosis is considered to have occurred with any unexplained death from 30 days after intracoronary stenting until end of trial follow-up.

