[†]The incidental angiographic documentation of stent occlusion in the absence of clinical signs or symptoms is not considered a confirmed stent thrombosis (silent occlusion)

‡Intracoronary thrombus

Symptomatic Graft Stenosis or Occlusion

Ischemic symptoms in the presence of \geq 50% diameter stenosis in a coronary bypass graft.

Unplanned Revascularization, Surgery, or Radiologic Procedure

Vascular access complications, sternal refixation or other complications requiring the subject to return to the cath lab or surgical rooms.

Disability After Stroke

In case of an event of stroke disability at 90-days±2 weeks will be an overall measurement of severity of stroke as assessed by mRS scale as defined in Section 16.1.3.

Left Main Equivalent Disease

Left main Medina classification 0, 1, 1 bifurcation disease (diameter stenosis of both the true ostial LAD and LCX [within 5 mm of the left main distal bifurcation]) \geq 50%, in the absence of significant angiographic stenosis in the left main coronary artery, may also be randomized if one

of the two following conditions are present:

- Both the ostial LAD and ostial LCX stenoses are \geq 70% stenotic by visual estimation, or
- If one or both of the ostial LAD and ostial LCX stenoses are \geq 50% and <70% stenotic by visual estimation, then this lesion(s) is demonstrated to be significant either by
 - a) non-invasive evidence of ischemia in its myocardial distribution; and/or
 - b) FFR ≤0.80; and/or
 - c) IVUS MLA ≤ 4.0 mm² (FFR is preferred).

Note: If both the ostial LAD and ostial LCX stenoses are \geq 50% and <70% stenotic by visual estimation, then both lesions must be significant by these criteria for the patient to be eligible for randomization.

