2.3.3 Other Secondary Endpoints

The following additional endpoints will be analyzed:

- The endpoint of all-cause death, myocardial infarction or stroke, in-hospital, at 30 days, 180 days, and at 1, 2, 4 and 5 years.
- The endpoint of all-cause death, myocardial infarction, stroke or unplanned revascularization for ischemia in-hospital, at 30 days, 180 days, and 1, 2, 4 and 5 years.
- All cause mortality, cardiac death and non-cardiac death in-hospital, at 30 days, 180 days, and 1, 2, 3, 4 and 5 years.
- Protocol-defined MI at 30 days, 180 days, and 1, 2, 3, 4 and 5 years.
- All MI (periprocedural, spontaneous, Q-wave, and non Q-wave) at 30 days, 180 days, and 1, 2, 3, 4 and 5 years.
- MI adjudicated per Universal MI definition at 30 days, 180 days, and 1, 2, 3, 4 and 5 years.
- Protocol-defined stroke at 30 days, 180 days, and 1, 2, 3, 4 and 5 years.
- All stroke, ischemic stroke, and hemorrhagic stroke in-hospital, at 30 days, 180 days, and 1, 2, 3, 4 and 5 years.
- Disability following stroke event at 90 days± 2 weeks
- Complete revascularization at baseline procedure, anatomic and functional
- Ischemia-driven revascularization in-hospital, at 30 days, 180 days, and 1, 2, 3, 4 and 5 years.
 - All Ischemia-driven repeat revascularization procedures.
 - Ischemia-driven target lesion revascularization (TLR)
 - Ischemia-driven target vessel revascularization (TVR)
 - Ischemia-driven non target vessel revascularization (Non-TVR)

- All revascularization (ischemia driven and non-ischemia driven) at index procedure, in-hospital, at 30 days, 180 days, and 1, 2, 3, 4 and 5 years.
 - All repeat revascularization procedures
 - o All TLR
 - o All TVR
 - All non-TVR
- Stent thrombosis (ARC definition) symptomatic or asymptomatic PCI arm only inhospital, at 30 days, 180 days, and 1, 2, 3, 4 and 5 years.
- Symptomatic graft stenosis or occlusion (since this requires angiographic documentation, this endpoint will be compared to symptomatic ARC definite stent thrombosis) CABG arm only in-hospital, at 30 days, 180 days, and 1, 2, 3, 4 and 5 years.
- Bleeding complications at 30 days, 180 days, and 1, 2, 3, 4 and 5 years.
 - Requirement for blood product transfusion
 - TIMI scale (major or minor)
 - BARC scale
- Time from randomization to procedure; time from index procedure to discharge; ICU days; time from index procedure to return to work

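### The planned comparison of graft failure with stent failure counts symptomatic stenosis of 50% or more in the CABG arm but only definite thrombosis in the PCI arm, so this unpowered secondary comparison is tilted against CABG by definition.

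*Protocol*

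**What the plan says.** Protocol 5.2 lists symptomatic graft stenosis or occlusion as a secondary endpoint and adds that, because it requires angiographic documentation, "this endpoint will be compared to symptomatic ARC definite stent thrombosis". Protocol 9.1.3 carries the same line. SAP 2.3.3 keeps it, marks the graft endpoint as belonging to one arm ("this endpoint will be compared to symptomatic ARC definite stent thrombosis) CABG arm only"), and schedules it in hospital, at 30 and 180 days, and yearly to 5 years.

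Protocol 16.2 defines the two sides.
- **CABG side:** ischemic symptoms together with at least 50% "diameter stenosis in a coronary bypass graft".
- **PCI side:** ARC definite stent thrombosis. The angiographic route needs a thrombus "that originates in the stent or in the segment 5 mm proximal or distal to the stent" plus at least one listed criterion within a 48-hour window. The pathological route needs recent thrombus at autopsy or in retrieved tissue.

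No endpoint called symptomatic in-stent restenosis is defined. Restenosis enters through the revascularization endpoints in Protocol 16.1.4, where "Target lesion revascularization is defined as any repeat percutaneous intervention of the target lesion or bypass surgery of the target vessel". Such a procedure is ischemia-driven if QCA shows at least 50% stenosis and one of several criteria is met, among them "Typical ischemic symptoms referable to the target lesion".

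**The concern.** The reason given for the pairing is that the graft endpoint requires an angiogram. That aligns how events are found, not what kind of failure counts. A bypass graft is charged for narrowing and for occlusion; a stent is charged only for thrombosis. A between-arm difference could then reflect the definitions rather than the treatments.

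The protocol sets a stricter standard elsewhere. Section 16.1.2 calls for one definition of MI in both arms so as to avoid ascertainment bias. Section 19.1 asks for the same complete-revascularization criteria in both arms. This comparison does not meet that standard.

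What is at stake is a secondary comparison of conduit durability, planned at every follow-up point to 5 years, which readers could take as evidence that stents fail less often than grafts.

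**Working it through.** The documents state no rate, sample size or power for this endpoint, so there is no planned figure to reproduce. The check is of definitions first, then an illustration.

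**Step 1. Apply the definitions to the same clinical picture.**

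| Finding at follow-up | CABG arm, this comparison | PCI arm, this comparison | PCI arm, elsewhere |
|---|---|---|---|
| Symptoms, conduit stenosis of 50% or more, no thrombus, treated medically | Event | No event | Not a revascularization event |
| Same, with a repeat procedure | Event | No event | Ischemia-driven TLR/TVR if the QCA criterion is met; also in the second powered composite as unplanned revascularization for ischemia |
| Symptomatic thrombotic occlusion of the conduit | Event | Event | Also TLR/TVR if a procedure follows |

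The arms differ in the first two rows. The revascularization endpoints in the last column apply to both arms, so they do not offset the difference in this comparison.

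**Step 2. Direction.** Let *r* be the rate of symptomatic conduit stenosis of 50% or more, or occlusion, assumed equal in both arms. Let *t* be the rate of symptomatic definite thrombosis in the PCI arm. The planned comparison sets *r* (CABG) against *t* (PCI). If definite thromboses are essentially a subset of the wider failure, *t* is at most *r*, and the definitions alone produce a difference of *r* − *t* against CABG.

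**Step 3. Illustration of the gap on the stent side.** Inputs are the XIENCE V arms of two trials in Protocol 2.7.1, with TLR as an assumed stand-in for the wider failure.
- SPIRIT IV: TLR 2.5%, definite or probable thrombosis 0.29%. Ratio 2.5 / 0.29 = 8.6; gap 2.5 − 0.29 = 2.21 points.
- COMPARE: TLR 1.7%, definite or probable thrombosis 0.7%. Ratio 1.7 / 0.7 = 2.4; gap 1.7 − 0.7 = 1.0 point.

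Limits: neither trial was confined to left main disease. TLR counts procedures, so it misses restenosis managed medically and includes procedures done for thrombosis. The thrombosis figures are definite or probable, wider than the definite category used here, which tends to understate the gap.

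**Step 4. What such a gap could do, if it applied.** Assume graft failure occurred at those TLR rates, stent failure were truly equal, and PCI were scored only for thrombosis. With n = 950 per arm (SAP 2.5.1), two-sided 0.05 (SAP 3.4) and p̄ the mean of the two rates,

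power = Φ{[(p₁ − p₂) − 1.96·√(2p̄(1 − p̄)/n)] / √([p₁(1 − p₁) + p₂(1 − p₂)]/n)}.

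- p₁ = 0.025, p₂ = 0.0029: about 98%.
- p₁ = 0.017, p₂ = 0.007: about 52%.

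These are conditional probabilities of a significant difference against CABG arising from the definitions alone. They are not forecasts, because no document gives a graft-stenosis rate.

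**The case against.** The strongest reply has four parts.

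- **The comparison carries little inferential weight.** This stands. It is unpowered and outside the testing order in Protocol 9.1.7.1 and SAP 3.10. Protocol 9.1.7.2 makes p-values for other endpoints descriptive and names stent thrombosis as an example of a time-to-event variable shown for hypothesis generation only. SAP 3.4.4 adds a caution. But that caution concerns chance; it does not address a bias with a fixed direction.
- **Restenosis is not ignored by the plan.** This also stands. A reader might infer that symptomatic restenosis after PCI is counted nowhere. The documents do not support that: when a repeat procedure follows, it is captured as ischemia-driven TLR or TVR and in the second powered composite. What is missing is its place in this comparison, and any stent-failure endpoint for restenosis managed medically, whose frequency is not given.
- **The rationale may be narrower than it looks.** The remark about angiographic documentation can be read as explaining why definite thrombosis was preferred to probable or possible. That is a fair reading, but it does not make the two events alike.
- **No single size can be claimed.** This stands. A reader might divide the 2.5% TLR in the left main study of Protocol 2.7.2 by the under-0.5% left main stent thrombosis in Protocol 8.3.2 ("Numerous prior studies of drug-eluting stents in subjects with ULMCA disease have demonstrated very low rates") and conclude that PCI failure is understated five-fold. The documents do not support that either. The two figures come from different studies, the first has only 174 subjects, and the second is an upper bound with no stated follow-up time. In the first study the listed components sum to 4.1 + 2.5 + 1.6 + 2.5 = 10.7%, below the 14.7% reported for their composite, so at least one of its figures is doubtful.

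**Conclusion.** The point holds as a minor one. As written, the comparison sets symptomatic stenosis or occlusion of grafts against thrombosis of stents, and so is tilted against CABG by definition. The direction rests on the two definitions in Protocol 16.2 and on the assumption that definite thromboses are essentially a subset of the wider stent failure. The size is unknown. The ratios of 2.4 and 8.6 show only that, in the protocol's own stent data, repeat procedures at the lesion were clearly more frequent than thrombosis. Study success, the powered secondary endpoints and their error control are untouched.

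**What to change.** Replace the single pairing in Protocol 5.2 and 9.1.3 and SAP 2.3.3 with two like-for-like comparisons:

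- (a) symptomatic graft occlusion against symptomatic ARC definite stent thrombosis;
- (b) symptomatic graft stenosis of 50% or more, or occlusion, against symptomatic in-stent restenosis of 50% or more or definite stent thrombosis. For restenosis, use the QCA-plus-symptoms criterion of Protocol 16.1.4 without requiring a repeat procedure.

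Word the symptom requirement and the method of measuring stenosis alike in both arms. At present 16.1.4 asks for symptoms referable to the lesion and for QCA, while the graft definition asks for neither. If this is not wanted, drop the cross-arm comparison and report each arm's rate descriptively under its own name.

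The cost is modest but more than a change of wording. Protocol 8.2 already sends all follow-up angiograms to the core laboratory, so no new imaging is needed. However, in-stent restenosis and graft occlusion alone need written definitions. SAP 4.3.3 lists only pre- and post-procedure QCA variables, so follow-up readings would have to be added. Symptoms would have to be linked to lesions, with some extra event classification. Comparison (b) will overlap with ischemia-driven TLR, and the report should say so.
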